### **PD-L1 Testing**

To ensure comparability of data across all studies of durvalumab and/or tremelimumab and to gain real world experience on the performance of this assay, it is strongly encouraged that all studies that include PD-L1 testing utilize the Ventana SP263 assay. Testing should be restricted to the Ventana SP263 assay and should be performed in accordance with the package insert on the Ventana Benchmark platform (Ultra or XT).

The Ventana SP263 assay is fully analytically validated test characterized through to the completion of reader precision studies in the non-small cell lung cancer (NSCLC) and squamous cell carcinoma of the head & neck (SCCHN). For these tumors, the Ventana SP263 assay has a fully reproducibility data package supporting cut-off and scoring algorithm. Following completion of ATLANTIC and HAWK clinical trials, the assay will be associated with clinical utility. In other cancer types (bladder, pancreatic, gastric, hepatocellular, triple negative breast, ovarian, esophageal, nasopharyngeal, glioblastoma, soft tissue sarcoma, cholangiocarcinoma, small cell lung, melanoma and cervical HPV + cancers), the Ventana SP263 assay has only limited clinical performance data.

### **Sample collection for PD-L1 testing**

- The preferred tumor sample for the determination of a patient's PD-L1 status is the one taken following the completion of the most recent prior line of therapy. Samples taken at this time reflect the current PD-L1 status of the tumor and considered

clinically most relevant.

- In AstraZeneca studies, the preferred sample for PD-L1 testing was less than or equal to 3 months old. In cases where a sample a less than 3 months old was not available, patients were asked to undergo a new biopsy if considered clinically appropriate by their treating physician.
- Samples should be collected via a core needle of 18 gauge or larger or be collected by an incisional or excisional tumor biopsy. Where institutional practice uses a smaller gauge needle, samples should be evaluated for tumor cell quantity (i.e., >100 tumor cells) to allow for adequate PD-L1 immunohistochemistry analyses.
- When the collection of a new sample is not clinically appropriate, archival samples may be utilized provided the specimen is not older than 3 years of age. When archival samples are used to assess PD-L1 status, the age of the sample/date of collection should be captured.
- Samples submitted for PD-L1 testing should be formalin fixed and embedded in paraffin. Samples from fine needle aspirates (FNA) or decalcified bone are not appropriate for PD-L1 analysis.

### **Sample data collection for PD-L1 testing**

The following fields of data should be collected from the site/institution collecting and if, indicated shipping of the samples:

- Patient identifier (e-code or unique identifier)
- Specimen identifier (written on the specimen)
- Site identifier
- Specimen collection date
- Type of specimen submitted
- Quantity of specimen
- Date of sectioning
- Archival of fresh tumor
- Tumor type
- Primary tumor location
- Metastatic tumor location (if applicable)
- Fixative

### **The following fields of data should be collected from PD-L1 testing laboratory:**

- Are the negative and positive controls stained correctly
- Is the H&E material acceptable
- Is morphology acceptable
- Total percent positivity of PD-L1 in tumor cells
- PD-L1 status (positive, negative or NA) in tumor cells

- Total percent positivity of PD-L1 in infiltrating immune cells

The Ventana SP263 assay to measure PD-L1 in tumors is experimental. As with all tests, there is a chance of false positive (the test shows high PD-L1 when it is not there) or false negative (the test does not show PD-L1 when it is there) results may occur.

### **Sample processing and if indicated submission process for PD-L1 testing**

#### Preparing Stored samples for testing

- Where samples already exist, they should be retrieved from the Biobank storage location. These blocks should undergo quality review, prior to evaluation or shipment. Where it is not possible or indicated to ship the block to a testing laboratory, unstained slides should be prepared from the paraffin-embedded tumor sample block (described below) prior to evaluation or shipment.

#### Preparing newly acquired samples for PD-L1 testing

- If patients are undergoing a biopsy procedure that provides the option to submit newly acquired samples, this sample should be used to determine PD-L1 status. Where clinically acceptable, a minimum of 2 core biopsies should be collected and processed to FFPE in a single block. The provision of 2 cores is advised in order to provide sufficient tissue for PD-L1 assessment.
- It is recommended that core needle tumor biopsies are collected using an 18 gauge or larger needle and the process should be image-guided. Excisional or incisional samples are also adequate. If this is not per the institutions normal practice and a smaller gauge needle is used then the number of cores collected should be increased to allow sufficient material for successful PD-L1 testing (>100 tumor cells) and embedded in the same block. If available, a single excisional biopsy of at least 4 mm in diameter may substitute for all core biopsies.

#### Fixation of biopsy samples for PD-L1 testing

- Previously frozen tissue is not acceptable for processing to FFPE for PD-L1 testing. To fix newly acquired tissue, place immediately (within 30 min of excision) into an adequate volume of 10% v/v neutral buffered formalin (NBF). Samples should remain in fixative for 24 – 48 hours at room temperature.
- It is vital that there is an adequate volume of fixative relevant to the tissue (at least a 10 volume excess) and that large specimens (if any) are incised prior to fixation to promote efficient tissue preservation.

#### Embedding in paraffin for PD-L1 testing

- An overnight processing schedule into paraffin wax is recommended

#### Storage of tumor blocks for PD-L1 testing

- FFPE blocks should be stored at ambient temperature and protected from light until shipment by courier at ambient temperature. FFPE blocks are stable under these conditions for an indefinite period.

Quality control of samples to be used for PD-L1 testing

- Tissue should be assessed by the site pathologist prior to PD-L1 testing.
- Each sample should be reviewed for:
  - Adequate fixation
  - Good preservation of morphology
  - Presence of tumor tissue
  - Histopathology consistent with indication
- Greater than 100 tumor cells are required to determine PD-L1 status – tumor cell content must be reviewed prior to testing in order for PD-L1 obtain a valid result.

If indicated, shipping samples to a PD-L1 testing laboratory

- When submitting sample to for PD-L1 testing the recommendation is to ship the block in order for sectioning to occur at the laboratory. Blocks should be shipped - containing enough material to be provided to allow a minimum of 5, and preferably 10, sections to be cut (each 4 microns thick) to be used for PD-L1 testing.

Sectioning instructions

Where it is not possible or indicated to ship the block to laboratory for PD-L1 testing, unstained slides should be prepared from the paraffin-embedded tumor sample block as described below:

- A minimum of 5-10 x 4 micron ( $\mu\text{m}$ ) thick, unstained sections should be provided for PD-L1 testing.
- A new disposable microtome blade must be used for each block to prevent contamination between patient samples.
- Slides are stable under these conditions for 6 months.
- Apply one section per slide to positively-charged Superfrost glass slides.
- The sections should be dried overnight between room temperature and 37°C. Do not dry sections at temperatures above 37°C.
- Sections should be stored at ambient temperature and protected from light until use or shipment to testing lab by courier at ambient temperature. It is recommended that slides are cut freshly prior to PD-L1 testing and they are used within 90 days of being cut to obtain PD-L1 status

### **8.3.4. Future biomarker studies and sample disposal**

An additional ICF will be issued to obtain consent for future biomarker research. All research performed with these samples will be subject to Ethical Committee evaluation

and approval.

**If future biomarker research is not consented samples will be kept at the central laboratory and then disposed of in five years.**

### **8.3.5. Withdrawal of informed consent for donated biological samples**

If a patient withdraws consent to the use of donated samples, the samples will be disposed of/destroyed, and the action documented. As collection of the biological samples is an integral part of the study, then the patient is withdrawn from further study participation.

The Principal Investigator:

- Ensures that biological samples from that patient, if stored at the study site, are immediately identified, disposed of /destroyed, and the action documented
- Ensures the laboratory(ies) holding the samples is/are informed about the withdrawn consent immediately and that samples are disposed/destroyed, the action documented and the signed document returned to the study site
- Ensures that the patient and the sponsor are informed about the sample disposal.

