m Fresh tumor biopsies: A fresh biopsy sample, optional, at the time of initial TUR. Those patients who have not achieved complete response will be submitted to a fresh biopsy, if not clinically contraindicated. It will be required to send fresh and formalin fixed samples of the pathological surgical specimen from patients who are candidate to salvage cystectomy.

n Urine samples (Optional): only for patients included in ICO L'Hospitalet. The samples will be collected at the time of screening period and the end of treatment visit. The first urine in the morning would be collected using a standard testing tube of 50 ml.

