#### **4.5. Withdrawal of patients from study**

Criteria for withdrawal of the study:

1. Withdrawal of informed consent
2. Death of the patient
3. Loss of follow-up

The investigator will do everything possible to keep all patients in the study unless it is considered that the most appropriate option for the patient is to interrupt his/her participation.

If a patient refuses to continue his/her participation in the study, all end-of-study evaluations should be performed if the patient accepts or can be evaluated. The date and reason for withdrawal should be recorded in the eCRF.

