#### **4.6. Withdrawal of consent**

Patients are free to withdraw from the study at any time (IP and assessments) without prejudice to further treatment.

Patients who withdraw consent for further participation in the study will not receive any further IP or further study observation, apart from follow-up for survival, which will continue until the end of the study unless the patient has expressly withdrawn their consent to survival follow-up. Note that the patient may be offered additional tests or tapering of treatment to withdraw safely.

A patient who withdraws consent will always be asked about the reason(s) for withdrawal and the presence of any AE. The Investigator will follow up AEs outside of the clinical study.

If a patient withdraws consent, they will be specifically asked if they are withdrawing consent to:

- all further participation in the study including any further follow up (e.g., survival contact telephone calls)
- withdrawal of consent to the use of their study generated data
- withdrawal to the use of any samples

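### Section 8.3.5 ends study participation when a patient withdraws only the use of donated samples, so outcome data that do not depend on those samples may go uncollected

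*Combined protocol and SAP*

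**What the plan says.** Protocol section 8.3.5 sets the trigger and the first consequence: "If a patient withdraws consent to the use of donated samples, the samples will be disposed of/destroyed, and the action documented". It then adds: "As collection of the biological samples is an integral part of the study, then the patient is withdrawn from further study participation". It makes no exception for optional samples or for samples already given.

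Section 4.6 separates the kinds of withdrawal. It introduces a list with "If a patient withdraws consent, they will be specifically asked if they are withdrawing consent to", and the list has three entries: further participation including follow-up, "withdrawal of consent to the use of their study generated data", and "withdrawal to the use of any samples". It also keeps survival follow-up going after withdrawal unless the patient has expressly refused it.

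Section 4.5, under "Criteria for withdrawal of the study", has three entries: withdrawn informed consent, death and loss to follow-up. It tells the investigator to try to retain patients, and asks for end-of-study evaluations from a patient who stops, if the patient accepts.

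The sampling itself is mixed. Schedule footnote m says "A fresh biopsy sample, optional, at the time of initial TUR", and section 8.1.1 makes urine collection optional and limited to one centre. A paraffin block is an entry criterion (section 4.1), and the four blood samples are covered by the main consent form and not called optional (section 8.3.1.1). The primary endpoint comes from the cystoscopic biopsy six weeks after radiotherapy (section 9.1).

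**The concern.** A patient who objects only to research use of tissue, blood or urine has not objected to being treated, assessed or followed. Section 8.3.5 nevertheless takes that patient out of the study. The three separate questions in section 4.6 have little purpose if one particular answer to the third also settles the first.

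The rule is also uneven. A patient who declines the optional fresh biopsy at the outset stays in the trial; one who gives it and later withdraws its use must leave.

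The trial's decision is a count of responders in 32 patients. An exit before the response cystoscopy either leaves an avoidable gap in that count or brings in a replacement patient. An exit afterwards cuts off disease-free and bladder-preservation follow-up.

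**Working it through.** **Where the rule bites, by time of withdrawal.** The schedule ends radiotherapy in week 8 and puts the response evaluation six weeks later. That is 8 + 6 = week 14, by inference; section 6 allows up to two weeks more.

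| Sample-only withdrawal occurs | Consequence under the text |
|---|---|
| Before 12 weeks of treatment are complete, no dose-limiting toxicity | Patient is replaced (section 6, replacement rule). The count stays at 32, but the analysed set depends on who kept sample consent |
| Before 12 weeks with dose-limiting toxicity, or after 12 weeks but before the cystoscopy | The early-exit clause does not provide a replacement; the primary outcome may be missing |
| After the cystoscopy | Primary outcome kept; disease-free and bladder-preservation follow-up stops; survival follow-up continues unless refused |

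In the second row the patient can still belong to the efficacy set, which needs only two durvalumab cycles and three weeks of radiotherapy (section 11.1.2). SAP Table 46 has a row for cystoscopy not done, but no rule for how that row enters the decision.

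**Does the outcome need the donated samples?** No. Response is read from the cystoscopic biopsy, and the later endpoints from cystectomy, recurrence, metastasis and death.

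**Size, for context.** The plan gives no figure for this point, so there is none to reproduce. I used the rule in section 11.3: continue with at least 6 responses in 12, positive with at least 19 in 32, at a response rate of 0.7.

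Power = Σ over x = 6…12 of P(X₁ = x) · P(X₂ ≥ 19 − x), with X₁ ~ Bin(12, 0.7) and X₂ ~ Bin(20, 0.7).

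For k missing results counted as non-responses, replace 20 by 20 − k (stage 2), or 12 by 12 − k with x = 6…12 − k (stage 1).

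| Missing results k | Power, all in stage 2 | Power, all in stage 1 |
|---|---|---|
| 0 | 0.909 | 0.909 |
| 1 | 0.877 | 0.851 |
| 2 | 0.830 | 0.761 |
| 3 | 0.764 | 0.631 |

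Both the range of k and the non-response convention are assumptions; the documents give neither. The starting value of 0.909 is not the planned 80%, because the written boundaries do not reproduce the stated error rates. That is a separate matter, and these figures should be read only as differences from 0.909.

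**The case against.** Several stronger readings are tempting, and the documents do not support them.

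- *The rule has no reason behind it.* Section 8.3.5 gives one, with partial support: the paraffin block is required for entry and blood sampling is not optional.
- *The samples serve only exploratory aims.* Biomarkers are listed in Table 8 as factors in the logistic regressions for the primary endpoint and for secondary objectives 1a and 1b, and PD-L1 enters the SAP's Cox models. The response outcome itself still does not depend on them, and the SAP already plans multivariate models that exclude PD-L1.
- *Outcome data are discarded and all follow-up is lost.* Section 8.3.5 orders destruction of samples, not data. Sections 4.6 and 8.1.5 keep survival follow-up, section 4.6 has adverse events followed outside the study, and section 4.5 seeks end-of-study evaluations. The week-12 list in section 8.1.3 does not include the cystoscopy, however, so the primary outcome is not secured by that route.
- *Sections 8.3.5 and 4.6 flatly contradict each other.* Section 4.6 lists questions and states no consequence for withdrawing samples alone. Section 8.3.5 could be read as supplying it, and as one form of the withdrawn consent in section 4.5. The conflict is by implication.
- *The results were affected.* No sample-only withdrawal is reported, and the SAP states that all 32 patients met the safety and per-protocol conditions. That does not show that every patient had the biopsy, but it gives no sign of harm.

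It is also fair to say that one missing result leaves power above the planned 80% under the written rule. What stands after all this is a stated rule that stops collection of outcomes for a reason unrelated to them.

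**Conclusion.** The point holds, as a minor one. Section 8.3.5 turns a limited withdrawal into an exit from the study, out of step with the separate options in section 4.6 and the list in section 4.5. What is exposed is the primary outcome when withdrawal precedes the cystoscopy (missing, or the patient replaced), and disease-free and bladder-preservation follow-up after that. Existing data and, by default, survival follow-up are not exposed.

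Each affected patient is 1/32 = 3.1% of the planned sample. One missing primary result costs 0.909 − 0.877 = 0.032 of power in stage 2, or 0.909 − 0.851 = 0.058 in stage 1, if counted as a non-response. The number affected is unknown and may be zero. The consent form was not available for review, so its wording on samples could not be compared.

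**What to change.** Replace the sentence in section 8.3.5 that ends participation with wording to this effect:

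*Withdrawing consent to sample use ends the use and further collection of research samples only. The patient remains in the study for clinical assessments, the response cystoscopy and biopsy, and follow-up, unless participation is separately withdrawn under section 4.6. Such a patient is not replaced for this reason and stays in the intention-to-treat analysis.*

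Add a cross-reference in section 4.6 and align the consent form. This wording covers assessment, follow-up and analysis. Section 4.4 lists withdrawal of consent as ending study drug without saying which kind, so that entry should be reconciled with the new text.

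The cost is a short amendment and incomplete biomarker data for that patient. Those data would be lost in any case, because the samples are destroyed.

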## **9. DISEASE EVALUATION AND METHODS**

The response to immunotherapy may differ from the typical responses observed with cytotoxic chemotherapy including the following (Wolchok et al 2009, Nishino et al 2013):

- Response to immunotherapy may be delayed
- Response to immunotherapy may occur after PD by conventional criteria
- The appearance of new lesions may not represent PD with immunotherapy
- SD while on immunotherapy may be durable and represent clinical benefit.

Based on the above-described unique response to immunotherapy and based on guidelines from regulatory agencies, e.g., European Medicines Agency “Guideline on the evaluation of anticancer medicinal products in man” (EMA/CHMP/205/95/Rev.4) for immune modulating anticancer compounds, the study may wish to implement the following in addition to standard RECIST 1.1 criteria:

- RECIST will be modified so that PD must be confirmed at the next scheduled visit, preferably, and no earlier than 4 weeks after the initial assessment of PD in the absence of clinically significant deterioration. Treatment with durvalumab + tremelimumab would continue between the initial assessment of progression and confirmation for progression.

- In addition, patients may continue to receive durvalumab + tremelimumab beyond confirmed PD in the absence of clinically significant deterioration and if investigators consider that patients continue to receive benefit from treatment.

Modification of RECIST as described may discourage the early discontinuation of durvalumab + tremelimumab and provide a more complete evaluation of its antitumor activity than would be seen with conventional response criteria. Nonetheless, the efficacy analysis will be conducted by programmatically deriving each efficacy endpoint based on RECIST 1.1 criteria.

Of note, clinically significant deterioration is considered to be a rapid tumor progression that necessitates treatment with anticancer therapy other than durvalumab + tremelimumab or with symptomatic progression that requires urgent medical intervention (e.g., central nervous system metastasis, respiratory failure due to tumor compression, spinal cord compression).

### **9.1. Efficacy variable**

The main efficacy variable of the study treatment is pathological response evaluated by biopsy performed via cystoscopy at the end of the treatment. Pathological response is defined as the absence of muscle-invasive bladder cancer at post-treatment biopsy ( $\leq$ cT1). Post-treatment biopsy will be performed by cystoscopy performed 6 weeks after the end of radiotherapy. Persistence of invasive cancer in the bladder is considered no response to therapy, and radical cystectomy, if feasible, would be indicated. Appearance of new lesions outside of the bladder is considered a first RECIST progression.

#### **Confirmation of progression guidelines are set for the following reasons:**

- for patient management and treatment decisions,
- in the absence of significant clinical deterioration, to promote the collection of additional scans after the first radiologic RECIST 1.1 assessment of progressive disease (PD) in order to distinguish pseudoprogression from true radiologic progression, also known as RECIST 1.1 modified for confirmation of progression,
- when scans are evaluated by Investigator and by BICR, to reduce informative censoring by Investigator assessments (Investigator assesses PD at a time-point earlier than does BICR).

Confirmed objective disease progression refers to either of the following scenarios: 1. clinical progression/deterioration followed by a radiologic verification scan (PD by RECIST 1.1); or 2. in the absence of significant clinical deterioration, radiologic PD by RECIST 1.1 followed by a second radiologic confirmation scan with PD assessed according to the specific confirmation of progression criteria listed below. RECIST 1.1 modified for confirmation of progression refers to the second scenario above. The

confirmatory scan should occur preferably at the next scheduled imaging visit and no earlier than 4 weeks following the date of the immediate prior assessment of RECIST 1.1 PD.

Immediate prior radiologic progression would be considered confirmed if any the following criteria are met in the confirmatory scan:

- $\geq 20\%$  increase in the sum diameters of target lesions (TLs) compared with the nadir at 2 consecutive visits, with an absolute increase of at least 5 mm in sum of diameters compared to nadir,
- and/or significant progression (worsening) of non-target lesions (NTLs) and/or of pre-existing new lesions at the confirmatory scan time-point compared with the immediate prior time-point (Note: Pre-existing new lesions are evaluated as NTLs at the confirmatory scan time-point),
- and/or additional new unequivocal lesions at the confirmatory scan time-point.

NOTE: In order to have confirmed objective disease progression, there should be two consecutive PD's, the first PD by RECIST 1.1 and the second PD using the confirmation of progression criteria (above). If the first PD by RECIST 1.1 is not confirmed, continue with assessments until the next PD by RECIST 1.1, which in turn will need its own immediate subsequent confirmation scan.

In the absence of significant clinical deterioration, treatment with study drug may continue between the initial assessment of progression and the scan to confirm progression.

If the confirmation scan confirms progression, then the date of the prior scan with PD should be declared as the date of progression.

If progression is not confirmed, in the absence of significant clinical deterioration, then the patient should continue study drug and on-treatment assessments until the next PD which will also require a follow-up confirmation scan. **If the first PD is not confirmed by the immediate next scan, then the Investigator should not change the PD assessment of the first scan.**

If a patient discontinues treatment (and/or receives a subsequent anticancer therapy) prior to radiologic progression, then the patient should still continue to be followed until confirmed objective disease progression.

